This primary outcome measures changes in number of migraine days per month before and during treatment. The number of migraine days per month will be captured using a validated headache questionnaire and scores as follows: 0-8 migraine days per month = low frequency episodic migraine, 9-14 migraine days per month = high frequency episodic migraine, 15-30 migraine days per month = chronic migraine.

[figure not shown]
Assessments of headache and sleep:

At screening (visit 1), headache severity and impact will be assessed based on patients' interviews and HIT-6. Sleep quality will be assessed using the Insomnia Severity Index.

(<https://cbtscience.files.wordpress.com/2014/02/insomniaseverityindex.pdf>).

On days 30, 60, 90 and 120, baseline and treatment impact on headache and sleep will be assessed using the Headache e-diary and the consensus sleep diary [Carney et al., (2012) *The consensus sleep diary: Standardizing prospective sleep self-monitoring*, Sleep Vol.35, No.2, pp.287-302], the latter of which captures total sleep time, sleep latency, wake after sleep onset, number of awakenings, quality, sleep efficiency, and trouble staying awake.

Study flow chart

B. Statistical Considerations

Sample Size Justification:

Although precise sample size calculations are difficult given the novelty of the hypotheses and hierarchical structure of the data, a simulation was created using the “SIMR” package in R and R-Studio. Enrolling $N = 100$ with 4 measurement occasions (baseline, M1, M2, M3) that are created by aggregating the daily measurements from each month provides sufficient power to detect even small associations between changes in sleep and migraine activity. For example, fitting a linear mixed effects model assuming a random intercept, a modest association between intercept and slope ($r = -0.50$), unit variances for the fixed and random effects (i.e., z-scores), and $\alpha = 0.05$, this sample size will provide 95% power (95%CI: 75.1% to 99.9%) to detect correlations between slopes (i.e., changes in migraine and sleep) as small as $r = 0.15$. Differences smaller than this magnitude are unlikely to be clinically meaningful.

Data Analysis:

To fulfill the study’s purpose, 4 hypothesis are being proposed:

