Hypothesis 1 – temporal relationship I: Fremanezumab partially prevents migraine by restoring some aspects of sleep disturbances. If this hypothesis is correct, fremanezumab-induced improvement in sleep disturbances will precede the improvement in headache (i.e., the reduction in migraine days per month).

Hypothesis 2 – temporal relationship II: Fremanezumab-induced improvement in sleep disturbances is secondary to the reduction in migraine days per month. If this hypothesis is correct, fremanezumab-induced reduction in migraine or headache days per month will precede the onset of improvement in sleep quality and quantity.

Hypothesis 3 – principle III: The prevention of migraine leads to improved sleep and reduced sleep disorders. If this hypothesis is correct, only fremanezumab responders will experience improved sleep or sleep disturbances whereas fremanezumab non-responders will not experience improvement of sleep disturbances. If this hypothesis is incorrect, sleep quality or quantity will not improve in fremanezumab responders.

Hypothesis 4 – principle IV: Fremanezumab-Improved sleep disturbances lead to reduced migraine or headache days per month. If this hypothesis is correct, only persons with improved sleep disturbances will experience reduction in number of migraine or headache days per month. If this hypothesis is incorrect, patients with improved sleep disturbances may be migraine treatment responders.

[figure not shown]
The primary analyses are designed to estimate the elements of the competing hypotheses (i.e., temporal changes in migraine and sleep). To contrast these hypotheses, we will employ multivariate multilevel regression models as summarized by MacCallum et al.⁷³ and Goldstein.⁷⁴ This approach to modeling within-person change does not have the limitations of a change score approach (i.e., unreliability of residualized change scores), or percentage change approaches (i.e., floor effects, heterogeneous variances) where predictors and outcomes are reduced to differences among measurement occasions. A multivariate modeling approach will allow a direct test of all study hypotheses while maintaining a conservative Type-I error rate. Briefly, parsimonious models will be specified for outcomes and lagged (Y_{t-1}) and synchronous (Y_t) representations of each of the proposed mechanisms modeling time with both linear and quadratic change parameters. This model form will

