capture the expected substantial early-treatment changes in mechanisms (emerging via reductions in daily headache probability and/or increased sleep quality), or more gradual changes that may occur over the full treatment period. The pre-treatment values and change parameters will be specified as individual-level random effects; this effectively allows a unique trajectory to be specified for each individual and for each outcome. These trajectories will then be aggregated using a series of fixed main effects and interactions that directly correspond to each of our specific hypotheses.

In hypothesis 1, lagged sleep trajectories (t-1, t-2, and t-3) are hypothesized to exhibit statistically significant associations with headache probability such that greater increases in sleep are associated with greater reductions in migraine activity. The opposite is assumed in hypothesis 2 where lagged headache trajectories are hypothesized to exhibit statistically significant associations with sleep such that greater reductions in migraine activity are associated with greater increases in sleep. The best fitting model, using lags of either/both will be estimated using nested models and likelihood ratio tests to evaluate the best fitting hypothesis.

Secondary analyses: In addition to testing primary hypotheses, this study will provide a rich source of data to examine effects on other mechanisms. First, analyses will consider questions of “for whom does treatment work?” We will test whether pre-treatment levels of outcomes lead to differential response to treatments (ie, association between intercepts and slopes), which could provide preliminary evidence that, for instance, individuals with worse sleep respond best to treatment. Second, we will estimate the primary models using additional dichotomizations such as ‘responders’ for both sleep and migraine activity (> 50% change). For these analyses, treatment phase (baseline, treatment) and responder (no, yes) will be fixed factors with associations between response groups evaluated using frequency counts and odds ratios (95%CI). In a final set of models, we will use three treatment phases (baseline, early treatment, late treatment) to examine the cross-lagged association of responders and non-responders by treatment phase.

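### The unit of t is undefined: on the plan's four monthly occasions the lag test of which improvement comes first is unidentified or nearly uninformative, and on days the stated power does not apply

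*Combined protocol and SAP*

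**What the plan says.** All of this is in B3 of the combined protocol and SAP.

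- **Sample Size Justification (B3.B).** The power figure rests on "4 measurement occasions (baseline, M1, M2, M3) that are created by aggregating the daily measurements from each month", with 100 participants. The simulated model is described by a random intercept, an intercept-slope association of -0.50 and unit variances. The claim is 95% power for a correlation between slopes of 0.15. No lag and no quadratic term is mentioned.
- **Data Analysis (B3.B), general description.** The models are multivariate and multilevel, are called parsimonious, and use synchronous terms and a single lag, "modeling time with both linear and quadratic change parameters". Then: "The pre-treatment values and change parameters will be specified as individual-level random effects".
- **Data Analysis, Hypotheses 1 and 2.** These ask whether the sleep improvement precedes the fall in migraine days per month, or the reverse. For Hypothesis 1, "lagged sleep trajectories (t-1, t-2, and t-3) are hypothesized to exhibit statistically significant associations with headache probability". For Hypothesis 2 the direction is reversed and no lag depth is given. The choice is made with nested models and likelihood ratio tests.
- **Overview (B3.A).** Sleep and migraine are recorded daily over about 120 days, and the design is called high-resolution. The Data Analysis section also speaks of daily headache probability.

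Nowhere is the unit of t stated.

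**The concern.** Hypotheses 1 and 2 are purely about temporal order, so the lag structure is the test. The month is a natural reading of t: it is the only occasion the plan defines, the hypotheses are worded in migraine days per month, and t-3 is exactly the longest lag that four occasions allow. On that reading there is too little left per person to separate three lags from an individual curved trajectory. The day is also a possible reading, but then the sample size text describes a different model.

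Either way, the analysis meant to discriminate between the two hypotheses is not both specified and powered. If unit, lag depth, rows and random effects stay open, they can be settled after the data are seen.

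**Working it through.** **1. The plan's own figure.** Inputs from Sample Size Justification: N = 100, alpha 0.05 (two-sided assumed), r = 0.15. The simplest version of a slope correlation gives power = Φ(atanh(0.15) × √97 − 1.96) = Φ(0.151 × 9.85 − 1.96) = Φ(−0.47) = 32% (44% one-sided). Treating all 400 person-months as independent gives Φ(0.151 × 19.92 − 1.96) = Φ(1.05) = 85%. A simulated random-intercept mixed model with unit variances and coefficient 0.15 gives 77%. I did not reproduce 95%. The simulation code is not in the plan, so the model behind the figure is unknown, and I treat that as a separate matter. What counts here is that its description contains neither lags nor quadratic change.

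**2. Months, with observed lagged predictors.** Rows per person T = 4 − longest lag. Observable variances and covariances per outcome = T(T+1)/2. Parameters = 6 (3×3 covariance of intercept, linear and quadratic effects) + 1 residual = 7. Rank is the number of those parameters that the data can determine.

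| Longest lag | Rows per person | Rows at N = 100 | Variances and covariances | Rank (of 7) |
|---|---|---|---|---|
| none | 4 | 400 | 10 | 7 |
| 1 | 3 | 300 | 6 | 6 |
| 2 | 2 | 200 | 3 | 3 |
| 3 | 1 | 100 | 1 | 1 |

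The trajectory model is identified without lags and fails at every lag. Taking both outcomes together at lag 1 does not help: 6×7/2 = 21 variances and covariances against 21 + 2 = 23 parameters. At lag 3 only month 3 remains, so time is constant and the fixed linear and quadratic terms drop out too; its lag-3 predictor is the untreated baseline month. Dropping the random quadratic term changes the lag-1 case: 3 + 1 = 4 parameters, 6 variances and covariances, rank 4.

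**3. Months, with one joint model of all four occasions.** Moments: 8 means + 8×9/2 = 44. Parameters: 6 means + 21 random-effect covariances + 3 residual terms + 6 lag coefficients = 36, rank 36, so it is formally identified. Precision at N = 100 needs assumptions: unit random-effect variances, intercept-slope correlation −0.50, between-outcome correlation 0.15, time running from 0 to 1 over the four occasions, and lag coefficients of size 0.15 in one direction and zero in the other.

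- Three lags: standard errors 2.5 to 2.9 with residual variance 1, and 1.2 to 1.4 with residual variance 0.25. Effect over standard error is 0.15/2.9 = 0.05 to 0.15/1.2 = 0.13, so power is barely above 5%. A joint test of the three coefficients on the same inputs, all at 0.15, is no better.
- Lag 1 only, quadratic terms kept: standard error 0.12 to 0.15. The ratio is 1.25 to 1.0, so power is about Φ(1.25 − 1.96) = 24% to Φ(1.0 − 1.96) = 17%.

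**4. Resolution.** Month 1 covers days 31 to 60. If sleep improves in the first week after injection and migraine in the third, both changes fall in the same occasion and appear synchronous.

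**5. Days.** With three daily lags, 120 − 3 = 117 rows per person, or 11,700 at N = 100. The random-effect covariance has rank 7 of 7 (already so on ten days). One simulated linear mixed model with lags 1 to 3 converged, with lag standard errors of about 0.009, assuming complete diaries. That shows such a model can be fitted; it is not a power calculation for a logistic headache model.

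**The case against.** The strongest reply is that the monthly occasions appear only in the sample size text, where the power figure is offered as an example. The analysis text never says that the lagged models use those aggregates. A daily record, a design called high-resolution and an outcome expressed as headache probability all fit days at least as well, and on days the model can be fitted. A figure next to the hypotheses is not visible in the text available to me and may carry more detail. This stands, and it is why the point is conditional on the unit of t.

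Three stronger readings are tempting and should not be drawn.

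- **That the planned test cannot be estimated or run at all.** This fails on the daily reading. On months it fails for the joint model, where the problem is precision, and for lag 1 with only a random intercept and slope. The general description does name one lag and promises parsimony, although the next sentences make the change parameters random.
- **That a three-lag monthly model collapses to a cross-sectional regression.** Month-3 headache regressed on earlier months' sleep is still a lagged regression, though a weak one.
- **That the likelihood ratio tests are invalid because the models use 300, 200 and 100 rows.** The plan does not say that different rows will be used, and fitting nested models to a common sample is routine. The plan only omits to say so.

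It is also fair to object that lags of one to three days address day-to-day carry-over rather than which treatment-related improvement comes first. That stands and shapes the fix.

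**Conclusion.** The concern holds in conditional form. The unit of t is not defined, and the lag depth is one in the general description but three under Hypothesis 1.

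- **If t is a month:** three lags with person-specific linear and quadratic change are not identified with observed lagged predictors (rank 6, 3 or 1 of 7). In a joint model they are nearly uninformative (standard errors about 1.2 to 2.9 against an effect near 0.15). The test would not discriminate between Hypotheses 1 and 2, and leads shorter than a month would be missed.
- **If t is a day:** the model can be fitted, but the stated 95% power does not describe it.

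The rank results assume unstructured random effects, as the text implies. The standard errors rest on the variances and the 0.15 lag coefficient assumed above, because the plan gives no values for the lagged model. This is more than missing detail, since neither reading gives a primary test of order that is both informative and covered by the stated power.

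**What to change.** In Data Analysis:

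1. State that the lag analysis uses the daily diaries, and give one lag depth for both directions. Use a logistic mixed model for headache day and a linear mixed model for one named consensus sleep diary variable. The Insomnia Severity Index, named as the primary sleep measure, is not listed as daily and cannot serve here.
2. Order each pair by clock time: last night's sleep before today's headache, and today's headache before tonight's sleep. This keeps the shortest lag in each direction out of the synchronous term.
3. State which random effects are kept, and fit all nested models to the same rows.
4. Run the same comparison on a longer scale from the same diaries, to address which treatment-related improvement comes first. Weekly bins counted from the first injection would give 4 full weeks before it (30/7) and 12 after (90/7): 16 bins, or 13 rows per person with three lags.
5. Keep the monthly aggregates for the before/after description and the slope correlation.

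In Sample Size Justification, state that the 95% figure refers only to the monthly slope correlation and not to the lag test.

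The cost is SAP wording, more model fitting and a narrower power statement. No new data are needed.

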Background about migraine and sleep: Most patients believe that many of their migraine attacks are triggered by sleeping too little, sleeping too much, have their sleep interrupted too many times during the night, poor sleep quality, not feeling well-rested in the morning hours after the sleep, etc. These common complaints gave rise to the notion that sleep disturbances are some of the most common triggers of migraine. Moreover, sleep disturbances may be a risk factor for chronification of migraine, the transformation of migraine from episodic to chronic form. If sleep disturbances can trigger migraine attacks or lead to its chronification, it is tempting to propose that drugs that prevent migraine may have an ability to restore normal sleep or attenuate certain aspects of sleep disturbances and by doing so, prevent the initiation of an attack by preventing or modifying its trigger.

Background on fremanezumab and the hypothalamus: Fremanezumab is an anti-CGRP monoclonal antibody and belongs to a class of drugs that effectively prevents migraine. In principle, the size of CGRP (about 150 kD) does not allow it to cross the blood brain barrier (BBB) and enter the brain. It is therefore believed to achieve its preventative effects by acting outside the brain. An exception to this thinking is the hypothalamus, a brain area where the BBB is relatively open and as a result, large molecules may gain some access to its neurons.

B3. DESCRIPTION OF RESEARCH PROTOCOL

A. Study Design – Overview, Methods, Procedures

Overview:

This is a within-person study design that examines treatment effects (changes) using high-resolution assessments. To complete the study, each participant will be observed using daily assessments of **migraine** and **sleep** outcomes before treatment (baseline: 0 to 30 days), and at 1, 2, and 3 months after treatment (injection 1: days 31-60, injection 2: days 61-90, injection 3: days 91-120). In essence, this creates an interrupted time-series design where repeated interventions are introduced at fixed intervals.

Methods:

The study involves 5 visits. The first and last visit will take place at the headache clinic, while the middle three will occur at the Clinical Research Center:

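### Without a control arm, the planned intercept-slope association cannot show who responds to fremanezumab, because zero is not its expected value when the drug has no effect

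*Combined protocol and SAP*

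**What the plan says.** Section B3.A (Overview) describes the design: "This is a within-person study design that examines treatment effects (changes) using high-resolution assessments". Everyone receives open-label fremanezumab after a 30-day baseline, and no placebo or untreated group is described.

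Section B3.B (Data Analysis) makes pre-treatment values and change parameters individual-level random effects, with linear and quadratic time, estimated by maximum likelihood. It prefers this to change scores. It states no residual correlation structure.

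Under Secondary analyses, the question of which patients benefit is to be answered as follows: "We will test whether pre-treatment levels of outcomes lead to differential response to treatments (ie, association between intercepts and slopes". The example given is that "individuals with worse sleep respond best to treatment", described as possible preliminary evidence. The association is given no reference value other than zero, and regression to the mean is not mentioned.

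The Sample Size Justification works with "4 measurement occasions (baseline, M1, M2, M3) that are created by aggregating the daily measurements from each month" and takes as a simulation input "a modest association between intercept and slope" of r = -0.50.

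**The concern.** The plan equates a statistical association (level with change) with a causal one (level with drug response). The equation holds only if, without any drug effect, level and change would be unrelated. Two ordinary mechanisms break that:

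- **Persistent fluctuation.** A person who enters during several bad weeks has a high fitted intercept and then drifts back. If the fluctuation outlasts one measurement occasion, a model with independent residuals assigns part of it to the person's intercept and slope.
- **Proportional non-drug improvement.** If everyone improves by the same percentage through placebo response, time or diary-keeping, those who start worse fall further in absolute terms.

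Both push the association in the direction the plan would read as worse patients responding best. That direction is negative whichever way the scale runs. A control arm would show how much of it to expect without the drug, and here there is none. At stake is a secondary claim about which patients benefit, which could be reported even if fremanezumab did nothing to sleep.

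**Working it through.** **Plan's own figure.** None is given for this test. The only computed figure in section B3.B is the power for a correlation between migraine and sleep slopes, which is a different quantity.

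**Inputs from the documents.** N = 100; four monthly occasions, one of them pre-treatment; alpha 0.05 (taken as two-sided); random intercept and change terms; maximum likelihood.

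**Assumed, not in the documents.** The stable share of variance between people (ICC), the month-to-month autocorrelation (rho), the non-drug decline, and no drop-out. The model below has linear change only; the quadratic term was not simulated.

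**Step 1: what the model removes.** With months t = 0, 1, 2, 3, the per-person intercept weights are (0.7, 0.4, 0.1, -0.2) and the slope weights are (-0.3, -0.1, 0.1, 0.3). H = (X'X)^-1 has entries 0.7, -0.3 and 0.2. A model with independent residuals estimates, in large samples, G = Cov(b) - s²H, where b holds the per-person fits and s² is the residual variance. Take total variance 1, half of it stable between people and half monthly fluctuation.

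- Independent fluctuation: the covariance of per-person intercept and slope is -0.3 x 0.5 = -0.15, and s² = 0.5. So G01 = -0.15 + 0.3 x 0.5 = 0. The model removes the artefact completely.
- Persistent fluctuation, rho = 0.5: var(intercept) = 0.5 + 0.5 x 0.96 = 0.980; var(slope) = 0.5 x 0.1975 = 0.09875; covariance = 0.5 x (-0.29625) = -0.148.
  - s² = [4 - (4 x 0.980 - 12 x 0.148125 + 14 x 0.09875)]/2 = (4 - 3.525)/2 = 0.2375.
  - G01 = -0.148 + 0.3 x 0.2375 = -0.077; G00 = 0.980 - 0.7 x 0.2375 = 0.814; G11 = 0.09875 - 0.2 x 0.2375 = 0.051.
  - r = -0.077/√(0.814 x 0.051) = -0.38, with no drug effect. The simulated median is -0.39.
- Same data, baseline-versus-treatment slope (x = 0, 1, 1, 1): G01 = -0.354 + 0.292 = -0.0625; G00 = 1 - 0.292 = 0.708; G11 = 0.514 - (4/3) x 0.292 = 0.125; r = -0.0625/√(0.708 x 0.125) = -0.21. The simulated median is -0.22. The bias is smaller but present.

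**Step 2: how often it is significant.** One-df likelihood ratio test, 300 runs per setting (standard error at most √(0.25/300) = 2.9 points). The figures are the percentage significant and negative on monthly data.

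| Stable / persistent / noise variance, rho | Linear slope | Phase slope |
|---|---|---|
| 0.5 / 0 / 0.5, independent | 6.7 | 4.7 |
| 0.7 / 0 / 0.3, independent | 2.3 | 2.0 |
| 0.5 / 0.3 / 0.2, rho 0.5 | 28 | 4.3 |
| 0.5 / 0.5 / 0, rho 0.3 | 42 | 5.3 |
| 0.5 / 0.5 / 0, rho 0.5 | 74 | 10.7 |
| 0.4 / 0.6 / 0, rho 0.7 | 84 | 12.7 |

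Milder persistence gives lower linear-slope rates: 18% rejections at ICC 0.8 and rho 0.3, and 10% with 30% measurement noise added (150 runs each). The highest monthly rate found was 92%. Fitted to daily data with independent residuals, the linear slope gave 16% at a day-to-day correlation of 0.2 and 80-100% with stronger persistence. The phase slope on daily data gave 26% to over 99%, so its protection applies to monthly data only.

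**Step 3: proportional non-drug decline.** If each person's expected level m falls to m(1 - ct) with the same c for all, the slope is -cm and its correlation with m is exactly -1, with no drug involved. For migraine-day counts with independent errors, the linear model gave a significant negative association in 42% of trials (falls of 5/10/15% over the three months), 52% (a 20% step), 73% (a 30% step) and 94% (10/20/30%). Another run with a common 20% decline gave 81%.

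**The case against.** The strongest reply is that the plan has already chosen the right tool. It avoids change scores, and its random-effects model holds an error rate of 2-7% when monthly residuals are independent. That stands.

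It also disposes of one tempting reading, that the association would usually be significant with no drug effect. Correlating the observed baseline with the raw change to the mean of M1-M3 gives an expected r = -(1-k)/√((1-k) x 4/3) = -0.866√(1-k) for month-to-month ICC k. That is -0.27, -0.47 and -0.61 at k = 0.9, 0.7 and 0.5, significant in 79% to over 99% of trials. But the plan does not propose that analysis, so those rates cannot be applied to it.

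Second, the high rates for the planned type of model need assumed persistence or an assumed non-drug decline. A phase slope, the coding the plan uses for its responder models, keeps the monthly rate low under persistence. This is also correct, but the plan does not specify phase coding for the intercept-slope test. It does not establish that residuals are independent, and its own hypotheses have sleep and migraine influencing each other across lags.

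Third, a reader might take the r = -0.50 in the Sample Size Justification as an admission that regression to the mean was expected. The documents do not support that: it is a simulation input with no stated source.

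Fourth, the analysis is secondary, hedged, and does not bear on the primary outcomes. That limits the consequence but does not make the reading valid.

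**Conclusion.** The concern holds as a problem of interpretation. In a one-group study, a negative intercept-slope association does not show differential response to fremanezumab, and zero is the right null only if residuals are independent and there is no baseline-proportional change from other causes. With no drug effect, the chance of a significant negative association in a linear random-slope model is about 2-7% under independent monthly residuals. It is roughly 10-70% (up to about 90%) under month-to-month persistence, and about 40-95% under a common proportional non-drug decline. With a phase slope on monthly data, persistence alone gives about 1-13%.

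These ranges rest on assumed ICC, autocorrelation and decline, on no drop-out, and on linear change. The documents do not show where in the range this trial would fall, so they do not support saying that a false finding is likely. They do support saying that the planned reading could not be told apart from one.

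**What to change.** In section B3.B, Secondary analyses:

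1. Describe the intercept-slope association as descriptive evidence of differential change, not of differential response to treatment, and delete the example about who responds best.
2. Fit the model with an autocorrelated residual structure, for example AR(1) on the daily diary data, and report the association with and without it. This addresses persistence only; it does nothing about non-drug decline, so item 1 is needed regardless.
3. Optionally, add an Oldham or Pitman-Morgan comparison of the baseline month with month 3 as a sensitivity check against regression to the mean. It held 3-8% under persistence.

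A significant Oldham result must not be used to restore the treatment claim. It rejected in 86% of runs under a common 20% non-drug decline. Individual effects unrelated to baseline can also mask or reverse it: with effects of SD 0.5 (monthly SD 1), power for a true 20% gradient fell from 47% to 6% at ICC 0.7 and from 97% to 9% at ICC 0.9. With no gradient it rejected in the wrong direction in 30-46% of runs. The SAP should state both limits.

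The cost is SAP wording and one or two further analyses of data already being collected. The downside is wider intervals and a weaker secondary conclusion.

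### The secondary responder analysis compares sleep and migraine over shared baseline and treatment windows, so natural co-fluctuation alone can favour Hypothesis 3 or 4; add a separated-window sensitivity analysis

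*Combined protocol and SAP*

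**What the plan says.** All references are to the combined protocol and SAP.

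- **Design (B3.A, Overview).** "This is a within-person study design that examines treatment effects (changes) using high-resolution assessments". There is no concurrent control. Migraine and sleep diaries cover the same days: "before treatment (baseline: 0 to 30 days), and at 1, 2, and 3 months after treatment".
- **Hypothesis 3 (B3.B, Data Analysis).** The pattern taken as support is that "only fremanezumab responders will experience improved sleep or sleep disturbances whereas fremanezumab non-responders will not experience improvement of sleep disturbances". Hypothesis 4 reverses the roles of sleep and migraine.
- **Responder analysis (B3.B, Secondary analyses).** Responder status is defined "for both sleep and migraine activity (> 50% change"), and "treatment phase (baseline, treatment) and responder (no, yes) will be fixed factors with associations between response groups evaluated using frequency counts and odds ratios".
- **Further models (same paragraph).** A last set divides treatment into an early and a late part and looks at cross-lagged associations of responders.
- **Primary analysis (B3.B, Data Analysis).** The multivariate multilevel model is said to test all the hypotheses directly, but lagged tests are spelled out only for Hypotheses 1 and 2.

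The plan names no separate window for the responder label and does not say which outcome may be compared by it.

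**The concern.** Responder status is itself a function of baseline and treatment data. Comparing sleep change between migraine responders and non-responders over the same two periods is clean only if sleep and migraine do not move together for reasons unrelated to the drug. The protocol expects the opposite: B2 presents poor sleep as a frequent migraine trigger.

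Suppose a participant has an unusually bad baseline month, with poor sleep and many attacks, followed by ordinary months. That person becomes a migraine responder whose sleep improved, even if the drug did nothing to sleep.

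This is the only described analysis that uses responder status, so it is the one a reader will match to the wording of Hypothesis 3. Hypotheses 3 and 4 are causal statements. An association produced by shared fluctuation could be reported as support for either.

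**Working it through.** **1. The plan's own figure.** The plan gives no operating characteristic for the responder analysis. Its only figure is "this sample size will provide 95% power (95%CI: 75.1% to 99.9"%) for "correlations between slopes (i.e., changes in migraine and sleep) as small as $r = 0.15". The interval matches the exact binomial interval for 19 successes in 20 simulated trials (75.13% to 99.87%). For 100 person-level slopes, Fisher's z gives atanh(0.15) x sqrt(97) - 1.96 = 0.1511 x 9.849 - 1.96 = -0.47, a power of about 31.9%. The 95% is not reproduced on that reading. This is a separate matter, and nothing below depends on it.

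**2. Inputs.**
- From the documents: N = 100 ("Enrolling $N = 100$ with 4 measurement occasions (baseline, M1, M2, M3) that are created by aggregating the daily measurements from each month"), 30 baseline days, 90 treatment days, a cut-off above 50%, alpha 0.05.
- Assumed, because the documents are silent: the within-person correlation rho between natural migraine and sleep fluctuation, its persistence and size, and a responder rate of about 30-35%.

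**3. Why shared windows matter.** Let B and T be the baseline and treatment means of migraine (M) and sleep (S). Then

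Cov(M_T - M_B, S_T - S_B) = Cov(M_T,S_T) + Cov(M_B,S_B) - Cov(M_T,S_B) - Cov(M_B,S_T).

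Take independent half-month blocks (2 baseline, 6 treatment) with fluctuation SDs s_M and s_S, and look at the fluctuation part only.
- Shared windows: rho x s_M x s_S x (1/2 + 1/6) = 0.667 x rho x s_M x s_S. The baseline supplies 0.5/0.667 = 75% of it.
- Treatment split early/late, baseline shared: the 1/2 term remains. Each change has variance (1/2 + 1/3) = 0.833 in units of its own squared SD, so the correlation of changes falls from rho to (0.5/0.833) x rho = 0.6 x rho, not to zero.
- All windows separate: every term pairs different blocks, so the sum is 0. Autocorrelation leaves a small remainder.

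**4. Half-month simulation** (2,000 trials per setting, no drug effect on sleep).
- logit p = -0.1 + 0.5z + a x U, plus (-0.8 + b x z') during treatment; migraine days ~ Binomial(15, p).
- ln(sleep disturbance) = 0.5z'' + 0.6V, with V = rho x U + sqrt(1 - rho^2) x U'. U and U' have autocorrelation 0.5.
- Main setting: a = 0.5, b = 0.8. Larger fluctuation: a = 0.7, b = 0.4. Drift: main setting plus an SD-1 person-level shift from baseline to treatment in both outcomes, correlated rho.
- Separated windows here: label from the first halves of baseline and treatment, sleep change from the second halves.

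False positives in the Hypothesis 3 direction (nominal 2.5%), shared / separated windows:

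| Setting | rho | Mean-change contrast | Odds ratio, both cut at 50% |
|---|---|---|---|
| Main | 0 | 2.7% / 1.9% | 2.5% / 2.0% |
| Main | 0.3 | 12.8% / 4.2% | 6.3% / 2.8% |
| Main | 0.5 | 29.7% / 5.0% | 10.4% / 4.6% |
| Larger fluctuation | 0.3 | 28.4% / 4.2% | 14.1% / 3.5% |
| Larger fluctuation | 0.5 | 67.6% / 5.7% | 29.0% / 4.2% |
| Drift | 0.3 | 24.9% / 10.7% | 15.0% / 7.8% |
| Drift | 0.5 | 58.0% / 23.2% | 31.2% / 14.0% |

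These odds-ratio results use a skewed diary measure (about 9% sleep responders without drift, 18% with it). On a 0-28 score almost nobody reaches 50% change, and the odds ratio rarely rejects.

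**5. Daily-level simulations** (two-sided, nominal 5%, mean sleep change).

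| rho | Shared windows |
|---|---|
| 0 | about 5-6% |
| 0.3 | 15-26% |
| 0.6 | 43-75% |

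Separated windows gave 4-7%. Splitting early and late treatment with a shared baseline gave 8-20% over rho 0.3-0.6.

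**6. The full Hypothesis 3 pattern** (significant improvement in responders, none in non-responders). It appeared in 15-56% of daily-level trials (rho 0.3-0.6). In half-month trials on a 0-28 score (rho 0.5 at most, 0.3 at least) it appeared in 9-21% (main) and 22-54% (larger fluctuation).

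**7. Size of the artefact.** On a 0-28 score at rho 0.5, mean change was -0.48 in responders and +0.24 in non-responders, a gap of 0.72 points. With larger fluctuation it was -0.89 and +0.37, a gap of 1.26. Both gaps are small beside the plan's seven-point insomnia bands (8-14, 15-21).

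**The case against.** **It is only secondary.** This stands. A reader might infer that the responder contrast decides Hypotheses 3 and 4. The documents do not say so: the analysis is listed as additional to the primary tests, and the multivariate model is presented as testing every hypothesis. The link to Hypothesis 3 rests on the shared word "responder" and on the lack of any other described analysis that uses it.

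**The named statistic is the odds ratio.** Partly stands. The odds ratio is less affected, and on a 0-28 score hardly at all. But the same sentence makes phase and responder fixed factors, and that contrast carries most of the bias.

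**The early/late models deal with it.** Partly stands. They separate the treatment periods but keep one baseline, and they add to the two-phase analysis without replacing it.

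**The rates are assumed.** This stands. No correlation is given, and at zero there is no inflation. The background describes sleep as a trigger, which is a directional idea and does not quantify non-causal co-fluctuation.

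**A same-outcome test would be significant by construction.** A reader might infer that the plan tests responder status on the outcome that defines it. The wording about associations between response groups reads more naturally as cross-outcome, so this calls for a clarifying sentence and is not an error.

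**Conclusion.** The concern holds in limited form. Any non-zero natural correlation between sleep and migraine biases the two-phase responder contrast towards Hypothesis 3 or 4. For mean sleep change at a nominal 5%, false positives run from about 5% at correlation 0 to roughly 15-26% at 0.3 and 43-75% at 0.6, given N = 100, about a third responders and the assumed persistence. These are rejection rates for one contrast. They should not be read as the chance of confirming Hypothesis 3, whose full pattern is less frequent.

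Nor should separated windows be read as a cure. If both outcomes share a lasting non-drug drift, 10.7% to 23.2% false positives remain against a nominal 2.5% (correlation 0.3 to 0.5). That part comes from the single-arm design. The primary lagged models are not put in question by this point. It is a cheap improvement to a secondary analysis and to how its result is worded.

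**What to change.** Add to section B3.B, before the data are analysed:

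1. **A pre-specified sensitivity analysis from the daily diaries.** Define migraine responders from baseline days 1-15 and month 1 (days 31-60), using days per diary day. Measure sleep change from baseline days 16-30 to months 2-3 (days 61-120). Mirror this for Hypothesis 4.
2. **A named sleep variable.** It must be a diary measure. The Insomnia Severity Index is given as the primary sleep outcome, but the assessment schedule lists it only at screening and uses the sleep diary on days 30-120, so it cannot supply half-month windows.
3. **Reporting.** Show it beside the planned analysis with estimates and confidence intervals. Do not require it to be significant. If the association appears only with shared windows, describe it as an association and not as support for the causal wording of Hypothesis 3 or 4.
4. **Clarification.** State that responder status is used only for the outcome that does not define it.
5. **Limitation.** State that a single-arm design cannot exclude shared persistent non-drug drift.

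The cost is SAP wording and programming, with no new data. The separated-window version has less power (61% falling to 24% in one simulated case with a true effect), which is why it should accompany the planned analysis and not decide it. Later responders will be misclassified, and the label is coarse: a participant at the entry minimum of 8 migraine days a month has about 8 x 15/30 = 4 in a half-month.
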